6.5. Study intervention compliance

When the individual dose for a participant is prepared from a bulk supply, the preparation of the dose will be confirmed by a second member of the study site staff.

When participants are dosed at the site, they will receive study intervention directly from the investigator or designee, under medical supervision. The date and time of each dose administered in the clinic will be recorded in the source documents. The dose of study intervention and study participant identification will be confirmed at the time of dosing by a second member of the study site staff other than the person administering the study intervention.

When participants self-administer the study intervention at home, compliance with study intervention dosing will be assessed by observed dosing with a site staff member as locally permitted using various forms of video calling (when at all possible) such as FaceTime, Skype, WhatsApp. In addition, compliance with study intervention dosing will be confirmed by counting returned tablets during the site visits and documented in the source documents and relevant form. Deviation(s) from the prescribed dosing regimen should be recorded.

A record of the quantity of VH3739937 CCI and / or placebo dispensed to and administered by each participant must be maintained and reconciled with study intervention and compliance records. Intervention start and stop dates will also be recorded.

6.6. Dose modification

No dose modifications are permitted in this study.

6.7. Continued access to study intervention after the end of the study

Given the lack of longer-term clinical benefit (Section 2.3.2), ViiV Healthcare recognizes the balance between the need to conduct an early phase monotherapy clinical study (for the larger and long term unmet medical need) and the need for HIV-1 infected treatment

naïve patients to receive cART as soon as possible after diagnosis. To meet both needs, this study design is efficient in screening (shortest period: approximately 7 to 14 days) and the monotherapy treatment with VH3739937 (period: 7 days). On study Day 8, following the scheduled blood collection as per SoA, participants will commence cART selected and prescribed by the investigator and sourced as per local requirements. After this time, the investigator is responsible for ensuring that participants continue to receive cART, whether or not the Sponsor is providing reimbursement for post-study treatment.

The Sponsor recognizes some HIV-1 infected adults may encounter barriers to accessing cART. Where it has been determined by the Investigator to be an acceptable option, participants receiving study treatment will have the option (but are not required) to receive reimbursement from the Sponsor for locally marketed ARVs (after the completion of dosing and through the study final follow-up visit) for up to a maximum of 90 days. The selection of ARVs will be investigator-chosen based upon local standard of care.

6.8. Treatment of overdose

An overdose is any dose of study intervention given to a participant that exceeds the planned, randomized dose for an individual within a given dose group.

In the event of an overdose, the investigator should:

- Evaluate the participant to determine, in consultation with the Medical Monitor, if possible, whether study intervention should be interrupted or whether the dose should be reduced.
- Closely monitor the participant for any AE/SAE and laboratory abnormalities until VH3739937 can no longer be detected systemically (at least 18 days), as medically appropriate.
- Obtain a plasma sample for PK analysis if requested by the medical monitor (determined on a case-by-case basis).
- Document the quantity of the excess dose as well as the duration of the overdose.

6.9. Prior and concomitant therapy

Concomitant medications (prescription and non-prescription) should be administered only as medically necessary during the study. Chemoprophylaxis for HIV-associated conditions is encouraged, if appropriate, at the discretion of the participant and their physician. All concomitant medications, blood products, and vaccines taken during the study will be recorded in the eCRF with dates of administration.

Because vaccines may cause a temporary increase in the level of HIV-1 plasma RNA, it is highly recommended that a vaccine, if necessary, be given at least 14 days prior to Screening. Please discuss with medical monitor if planned to give during this time.

Any medication or vaccine (including over-the-counter or prescription medicines, vitamins, and/or herbal supplements) that the participant is receiving at the time of enrolment or receives during the study must be recorded along with:

- Reason for use

- Dates of administration including start and end dates
- Dosage information including dose and frequency

The medical monitor should be contacted if there are any questions regarding concomitant or prior therapy.

6.9.1. Permitted Medications:

1. Acetaminophen/paracetamol at doses of ≤ 2 g/day or NSAIDs are permitted for use any time during the study and their use documented in the CRF.
2. In the event of irritation from ECG leads, up to 2.5% topical hydrocortisone may be used at the discretion of the investigator.
3. Any vaccine, including those available and approved for SARS-CoV-2 and other non-HIV vaccines should be administered at least 14 days prior to Screening. Please discuss with Medical Monitor if planned to give during the study period.
4. Other concomitant medications may be considered on a case by case basis by the investigator in consultation with the medical monitor if required.

Concomitant medications (prescription and non-prescription) should be administered only as medically necessary during the study. Participants must notify their Investigator of any current or proposed concomitant medication, whether prescribed or over-the counter because of the potential for interactions between such treatments and the study medications.

6.9.2. Prohibited Medications and Non-Drug Therapies

The following concomitant medications or therapies are not permitted at any time during the study:

- HIV immunotherapeutic / immunomodulatory vaccines are not permitted at any time during the study.
- Other experimental agents, antiretroviral drugs not otherwise specified in the protocol, cytotoxic chemotherapy, or radiation therapy may not be administered.
- Systemically administered immunomodulators (such as interleukin and interferon agents) are prohibited. This includes topical agents with substantial systemic exposure and systemic effects. Use of topical imiquimod is permitted.
- Chronic use of systemic (oral or parenteral) glucocorticoids must be avoided due to immunosuppressive effect; however, short treatment courses (e.g., 14 days or less) of oral prednisone/ prednisolone/methylprednisolone are allowed. Topical, inhaled or intranasal use of glucocorticoids will be allowed.
- Acetaminophen (paracetamol) cannot be used in patients with acute viral hepatitis [James, 2009].
- Participants must abstain from taking prescription or non-prescription drugs (including vitamins, recreational drugs, and dietary or herbal supplements) within 7 days (or 14 days if the drug is a potential enzyme inducer) or 5 half-lives

(whichever is longer) before the start of study intervention until completion of the final visit on Day 25, unless, in the opinion of the investigator and sponsor, the medication will not interfere with the study.

- Narrow therapeutic index drugs that are substrates of P-gp or CYP3A are not permitted during study.

7. DISCONTINUATION OF STUDY INTERVENTION AND PARTICIPANT DISCONTINUATION/WITHDRAWAL

Discontinuation of specific sites or of the study as a whole are handled as part of [10.1](#).

7.1.1. Liver chemistry stopping criteria

Discontinuation of study intervention for abnormal liver tests is required by the investigator when a participant meets one of the conditions outlined in the algorithm or in the presence of abnormal liver chemistries not meeting protocol-specified stopping rules if the investigator believes that it is in best interest of the participant.

Liver Chemistry Stopping Criteria Algorithm

Refer to Section 10.6 for required Liver Safety Actions and Follow-up Assessments

7.1.2. QTc Stopping criteria

If a clinically significant finding is identified (including, but not limited to, changes from baseline in QT interval corrected using Fridericia's formula [QTcF]) after enrollment, the investigator or qualified designee will determine if the participant can continue the study intervention and if any change in participant management is needed. This review of the ECG printed at the time of collection must be documented. Any new clinically relevant finding should be reported as an AE.

The QTcF correction formula must be used for each individual participant to determine eligibility for and discontinuation from the study.

The Baseline QTcF should be based on average QTcF values of triplicate electrocardiograms obtained over a brief (e.g., 5-10 minute) recording period from the Day 1 pre-dose ECG.

The average of triplicate ECG readings is the preferred method for confirmation of stopping threshold.

A randomized participant who develops an on-treatment QTcF >500 msec or an increase from baseline QTcF >60 msec should have two repeat unscheduled ECGs within 10 minutes. Using these triplicate ECGs, if the average QTcF >500 msec or an increase from baseline QTcF >60 msec, the participant will be withdrawn from the study. Finally, this participant should have repeated unscheduled ECGs until their QTcF measurement returns to their original averaged QTcF value at Day 1 pre-dose.

For participants with underlying bundle branch block, follow the discontinuation criteria listed below:

| Baseline QTcF with Bundle Branch Block | Discontinuation QTcF with Bundle Branch Block |
|--|---|
| < 450 msec | > 500 msec |
| 450 – 480 msec | ≥ 530 msec |

7.1.3. Individual Participant Laboratory Abnormality and Adverse Event Stopping Criteria

Investigators should make every effort to have a discussion with the Medical Monitor before the next dose to help assess if the study intervention should be stopped. Individual participant laboratory abnormality and AE stopping criteria for the study, as follows:

| | |
|---------------|---|
| Adverse Event | 
 Any clinically significant AE deemed to require discontinuation of the IP Any related Grade 3 or any Grade 4 rash Grade 2 rash with evidence of systemic involvement Grade 2 or higher rash with concurrent fever, AST/ALT elevation or eosinophilia prior to the follow up phase will be withdrawn from study intervention Grade 3 or higher allergic reaction Any Grade 3 or higher Psychiatric AE. The investigator will discontinue the participant from the study and arrange for emergency psychiatric evaluation/management; the panel for drugs of abuse will be tested New onset suicidal ideation as clinically diagnosed by the Investigator (in consultation with psychiatry, if needed). The Investigator will discontinue the participant from the study and arrange for emergency specialist psychiatric evaluation/management Any Grade 3 or higher AE related to study medication Any Grade 4 AE or laboratory abnormalities (with the exception of an asymptomatic grade 4 cholesterol, triglyceride or CPK increase) A participant meets the QTcF stopping criteria described in Section 7.1.2 Moderate to severe (as clinically determined by the investigator) COVID-19 infection (suspect, probable, or confirmed using the most recent version of the WHO case definition) |
|---------------|---|

7.1.4. Temporary discontinuation

Withdrawal of study treatment, including any missed dose on Days 1 to 7 **CCI** [REDACTED], requires withdrawal from the study. See Section [7.2](#) for further detail.

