7.2. Participant discontinuation/withdrawal from the study

A participant may withdraw from the study at any time at the participant's own request for any reason (or without providing any reason).

A participant may be withdrawn at any time at the discretion of the investigator for safety, behavioral, or compliance reasons.

Investigators will attempt to contact participants who do not return for scheduled visits or follow-up.

At the time of discontinuing from the study, if possible, an ED visit should be conducted together with a follow-up visit approximately 18 days after the last dose of study intervention, as shown in the SoA. See SoA for data to be collected at the time of study discontinuation and follow-up and for any further evaluations that need to be completed. A participant who is withdrawn from the study for any reason related to safety (listed in Section [7.1](#) or otherwise) will continue to be followed up to assess the outcome of the safety event that triggered discontinuation of study drug. If a participant is unable to return to the clinic for any reason, site staff are encouraged to contact the participant for assessment of AEs.

The participant will be permanently discontinued from the study intervention and the study at that time.

All data and samples collected up to and including the date of withdrawal of/last contact with the participant will be included in the study analyses. If the participant withdraws consent for disclosure of future information, the sponsor may retain and continue to use any data collected before such a withdrawal of consent.

If a participant withdraws from the study, the participant may request destruction of any samples taken and not tested, and the investigator must document this in the site study records.

The primary reason for participant discontinuation/ withdrawal from the study will be documented in the eCRF based on the list below:

| Reasons | Additional items/Sub-reasons |
|--|--|
| AE | Unsolicited AE Solicited AE |
| Lost to follow-up | Subject Relocated Subject was Incarcerated Other, specify Unknown |
| Participant Reached Protocol-Defined Stopping Criteria | Liver Event QTc Laboratory Abnormality |
| Physician Decision | Loss of ability to freely provide consent due to treatment of either a psychiatric or physical condition |
| Pregnancy | |
| Protocol Deviation | Repeat non-adherence of participant with protocol requirements or treatment |
| Site Terminated by Sponsor | |

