8.3.6. Suicidal ideation and behavior risk monitoring

VH3739937 is not a central nervous system active drug nor is it being developed for a neurologic or psychiatric condition. However, given the risk of suicidal ideation at supratherapeutic doses identified in one study with another MI, GSK3532795, all participants will undergo assessment for suicidality in this study. Any clinically diagnosed case of suicidality (using the C-SSRS as tool during Screening, on-treatment, and in follow-up) will result in exclusion from the trial or (if already randomized) immediate discontinuation from the study. Moreover, in these cases, the Investigator will arrange for urgent psychiatric evaluation and management.

Participants with HIV infection occasionally may present with symptoms of depression and/or suicidality (suicidal ideation or behavior). In addition, there have been some reports of depression, suicidal ideation and behavior (particularly in patients with a pre-existing history of depression or psychiatric illness) in some patients being treated with other ARTs such as INSTIs, including DTG. Therefore, it is appropriate to monitor participants for suicidality before and during treatment.

Participants being treated with VH3739937 should be monitored appropriately and observed closely for SIB or any other unusual changes in behavior, especially at the beginning and end of the course of intervention, or at the time of dose changes, either increases or decreases. Participants who experience signs of SIB should undergo a risk assessment. All factors contributing to SIB should be evaluated and consideration should be given to discontinuation of the study intervention. It is recommended that the investigator consider mental health consultation or referral for participants who experience signs of suicidal ideation or behavior. Participants presenting with new onset/treatment emergent depression should be advised to contact the investigator immediately if symptoms of severe acute depression (including suicidal ideation/attempts) develop, because medical intervention and discontinuation of the study medication may be required.

When informed consent has been given, families and caregivers of participants being treated with VH3739937 should be alerted about the need to monitor participants for the emergence of unusual changes in behavior, as well as the emergence of SIB and to report such symptoms immediately to the study investigator.

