10.7. Appendix 7: Toxicity Management

Adverse events that occur during the study should be evaluated by the investigator and graded according to the DAIDS toxicity scales (see Section 10.8). Additional information regarding detecting, documenting and reporting AEs and SAEs are available in Section 10.3.

Study drug may be interrupted at the discretion of the investigator and according to the severity of the AE.

No toxicity-related dose reductions of study drugs will be allowed. Guidance is provided below on subject management and study drug interruptions based on the severity of the AE for specific toxicities. All changes in study drug must be accurately recorded in the participant's eCRF.

Grade 1 or Grade 2 Toxicity/Adverse Event

Participants who develop a Grade 1 or Grade 2 AE or toxicity may continue study treatment at the discretion of the investigator. Participants who choose to withdraw from the study due to a Grade 1 or 2 AE should have study withdrawal and follow-up evaluations completed.

Grade 3 Toxicity/Adverse Event

Participants who develop a Grade 3 AE or toxicity should be managed as follows:

If the investigator has compelling evidence that the Grade 3 AE or toxicity has not been caused by study treatment, dosing may continue after discussion with the medical monitor.

Participants who develop a Grade 3 AE or toxicity that the investigator considers related to the study drugs should have study treatment permanently discontinued and be rechecked each week (at minimum) until the resolution of the AE.

Participants with asymptomatic Grade 3 laboratory abnormalities should be investigated for all potential non-drug related causes, and, following discussion with the medical monitor, may continue study drug if the investigator has compelling evidence that the toxicity is not related to study treatment.

Grade 4 Toxicity/Adverse Event

Participants experiencing Grade 4 AEs requiring permanent discontinuation of study treatment should be followed weekly until resolution of the AE and encouraged to complete the withdrawal and follow-up study evaluations as noted above.

Specific Toxicities/Adverse Event Management

General guidelines for the management of specific toxicities that are considered to be related or possibly related to study treatment are provided below.

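### For once-daily cohorts, Appendix 7 permits drug interruptions that 7.1.4 and 7.2 turn into permanent withdrawal; separately, 6.8 offers a post-overdose dose reduction that 6.6 bars

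*Protocol*

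**What the plan says.** Protocol 7.1.4, headed as temporary discontinuation, treats "Withdrawal of study treatment, including any missed dose on Days 1 to 7" as requiring withdrawal from the study and points to 7.2. The words immediately after the day range are redacted. Section 7.2 adds: "The participant will be permanently discontinued from the study intervention and the study at that time". Section 7.1, with no redaction at this point, counts anyone who has not had every planned dose as discontinued, and says that a participant whose drug is permanently stopped does not stay in the study.

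Appendix 7 (10.7) takes a different line: "Study drug may be interrupted at the discretion of the investigator and according to the severity of the AE". It then announces: "Guidance is provided below on subject management and study drug interruptions based on the severity of the AE for specific toxicities". On reductions it is firm: "No toxicity-related dose reductions of study drugs will be allowed".

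Section 6.6 says: "No dose modifications are permitted in this study". Section 6.8, which covers overdose only, asks the investigator to determine, with the Medical Monitor if possible, "whether study intervention should be interrupted or whether the dose should be reduced".

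**The concern.** A site managing an adverse event will open the toxicity appendix. It finds permission to interrupt and no warning that a missed dose ends participation. Section 7.1.3 asks investigators to try to speak with the Medical Monitor before the next dose, and 10.7 lets dosing continue after an unrelated Grade 3 event once that conversation has taken place. Holding a daily dose while waiting for the call is therefore plausible. The site then either loses a participant whose event did not require stopping, or resumes dosing against 7.1.4.

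In the overdose case, a site that takes up the reduction offered in 6.8 breaks 6.6. A site that takes up the interruption may break 7.1.4.

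What is at stake is an avoidable loss or deviation in cohorts of 6 active participants. Under SAP Table 1, a missed dose (criterion 01) or an incorrect dose (criterion 02) excludes the participant from the Per-Protocol set.

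**Working it through.** No power, alpha or sample-size figure is involved. The check compares texts and then counts how many doses a correction could still reach.

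**Step 1: does 10.7 deliver the interruption guidance it announces?** Its rule blocks, in order:

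| Block in 10.7 | Direction to the site |
|---|---|
| Grade 1 or 2 event | May continue |
| Grade 3 event | Continue if there is compelling evidence that it is unrelated, after Medical Monitor discussion; permanently stop if related |
| Grade 4 event | Follow-up after permanent stop |
| Liver chemistry | Refers to the stopping criteria in 7.1.1 and 10.6 |
| Lipids | Continue if asymptomatic |
| CPK | Recheck; stop and withdraw for persistent, related Grade 4 |
| Rash Grade 1 | May continue |
| Rash Grade 2 | Continue if isolated; permanently stop if systemic involvement |
| Rash Grade 3 or 4 | Permanently stop for related Grade 3 or any Grade 4 |

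There are 9 blocks, and 0 of them describe hold-and-resume. The appendix has its own term for permanent discontinuation, so interruption in its opening text reads naturally as a temporary hold.

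**Step 2: is an interruption a missed dose?** Protocol 4.1 has study drug taken each morning within a 2-hour window. A delay inside that window need not be a missed dose. A daily dose held for the day is one, and 7.1.4 with 7.2 then applies. A single-dose cohort has no dose after Day 1 to hold, so this conflict concerns once-daily cohorts only.

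**Step 3: dose changes.** Section 6.6 allows none. Appendix 7 bars toxicity-related reductions and so agrees with 6.6. The reduction offered in 6.8 is the provision out of line. The interruption also offered in 6.8 meets 7.1.4 in the same way as in Step 2.

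**Step 4: reach.**
- Part 1A, once daily (Protocol 4.1): 6 + 6 + 1 = 13 of the 20 Part 1 participants. The footnote to SAP 4.7 says the Part 1 interim has taken place, so a correction cannot help them.
- Part 2 (SAP 1.2): 6 active + 1 placebo = 7 participants, with the dosing regimen redacted.
- If Part 2 is once daily, the doses after Day 1 (Days 2 to 7) number 7 × 6 = 42, of which 6 × 6 = 36 are active.
- If Part 2 is single dose, the number is 0.

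These are counts of doses that could be held, not expected events. The documents give no interruption rate.

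**The case against.** The best counter-argument is that 10.7 grants a permission and 7.1.4 states its consequence: the investigator may hold for safety, and a resulting missed dose ends participation. Every operative rule in 10.7 already says continue or stop, and contact with the Medical Monitor is encouraged before the next dose. This lowers the chance of misapplication. It does not remove the defect, because 10.7 never states the consequence and announces guidance on interruptions that it does not give.

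The redaction in 7.1.4 is a fair limit. Hidden words that exempted investigator holds would dissolve the first conflict. Sections 7.1 and 7.2 give no sign of such an exemption.

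Four stronger readings are tempting, and the documents do not support them.
- **That 8.3.6 is a further contradiction**, because it mentions monitoring "or at the time of dose changes, either increases or decreases". The title of Table 3 in the Protocol's list of tables refers to a loading dose, so a scheduled dose change cannot be excluded, and that would not be a modification under 6.6. Section 8.3.6 permits no change; it only asks for closer observation when one occurs.
- **That the SAP's pharmacokinetic rules wrongly assume dosing resumes after a missed dose.** SAP 4.3.1.3 and 4.6.2 also cover incorrect doses, after which a legitimate next dose can follow.
- **That the lost participant could not be replaced.** SAP 4.1.1 excludes replacement for a safety concern. Protocol 4.1 bars it when stopping criteria are met and allows it for non-safety reasons. A hold for an event that met no stopping criterion is not clearly settled by either, so non-replacement is not established.
- **That the primary viral-load estimate is distorted.** Without an interruption rate nothing supports this. The primary analysis uses the Full Analysis Set with available data and no imputation.

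**Conclusion.** Both conflicts stand in the current text: the interruption permission in 10.7 against 7.1.4 with 7.2, and the dose reduction in 6.8 against 6.6. They are errors of wording, not missing detail, and they are minor.

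The practical consequence is an unintended withdrawal or a dosing deviation among any remaining once-daily participants, with at most 42 doses exposed in Part 2 and possibly none. Protocol 4.1 aims for at least 5 evaluable participants per active cohort, so a cohort of 6 tolerates one loss (6 − 5 = 1).

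The conclusion rests on three assumptions: the redacted qualifier in 7.1.4 does not exempt investigator holds; interruption in 10.7 means a temporary hold; and, for the correction to have any benefit under 10.7, Part 2 is once daily with dosing still to come.

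**What to change.** In 10.7, delete the sentence "Study drug may be interrupted at the discretion of the investigator and according to the severity of the AE" and take the reference to study drug interruptions out of the sentence that announces guidance. Add a cross-reference such as: *A missed dose is handled under Section 7.1.4 and requires withdrawal as described there.* If the rule itself is restated, use 7.1.4's full wording with its qualifier, so that single-dose cohorts are not misdescribed.

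In 6.8, replace the choice between interrupting and reducing with: *continued or permanently discontinued (see 6.6 and 7.1.4)*.

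Leave 8.3.6 unchanged, since deleting its wording could remove suicidality monitoring at a planned dose transition. Make no change to the SAP. The investigator's grounds for stopping for safety under 7.1.3 are untouched.

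The cost is a few lines of text, with no new data or analysis. Amendment 1 made the same kind of alignment among 7.1, 7.1.3 and 10.7. Under Protocol 10.1.1 a protocol amendment goes to the IRB/IEC, so these edits should be bundled with the next one. A separate amendment is not warranted if Part 2 is single dose or its dosing is complete.
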